Procedure	Days -28 to -2	Day -1	Day 1	3 to 14 days	Day -1	Day 1	Within 28±2 days after last study treatment		
Urine Drug Screen	X								Additional tests can be done at the discretion of the investigator.
PK (Glucagon)			Pre-hypoglycemia induction, Predose, 5, 10, 15, 20, 25, 30, 40, 50, 60, 90, 120, 240 min			Pre-hypoglycemia induction, Predose, 5, 10, 15, 20, 25, 30, 40, 50, 60, 90, 120, 240 min	X	X	Sampling times are relative to the time of study treatment administration (0 min). Predose time point will be between insulin infusion stop and study treatment.
Plasma Glucose for PD			Pre-hypoglycemia induction, -5, Predose, 5, 10, 15, 20, 25, 30, 40, 50, 60, 90, 120, 240 min			Pre-hypoglycemia induction, -5, Predose, 5, 10, 15, 20, 25, 30, 40, 50, 60, 90, 120, 240 min			-5 mins = stop insulin infusion. Sampling times are relative to the time of study treatment administration (0 min). Predose time point will be between insulin infusion stop and study treatment.
Genetic Sample (Stored)		X							Single sample for pharmacogenetic analysis taken prior to/on Period 1 Day -1.

	Screening		Period 1	Wash out		Period 2	Follow-up/ED	Additional Follow-up for TE ADA ^a	Comments
Procedure	Days -28 to -2	Day -1	Day 1	3 to 14 days	Day -1	Day 1	Within 28±2 days after last study treatment		
Anti-glucagon Antibodies			Pre-hypoglycemia induction				X	X	In the event of drug hypersensitivity reactions (immediate or non-immediate), samples will be collected as close to event onset as possible, at event resolution, and 30 days following the event. Patients with TE ADA at follow-up/ED will undergo additional follow-up. Refer to Section 9.7.1 for details.
Health Outcome Instruments									
Clarke Hypoglycemia Awareness Survey		X							
Nasal and Non-nasal Score Questionnaire			Pre-hypoglycemia induction, 15, 30, 60, 120 min			Pre-hypoglycemia induction, 15, 30, 60, 120 min			Sampling times are relative to the time of study treatment administration (0 min). Questionnaire will be collected in both LY900018 and IMG treatment groups in both periods.

	Screening		Period 1	Wash out		Period 2	Follow-up/ED	Additional Follow-up for TE ADA ^a	Comments
Procedure	Days -28 to -2	Day -1	Day 1	3 to 14 days	Day -1	Day 1	Within 28±2 days after last study treatment		

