3.1. Study Rationale

Nasal glucagon (LY900018) is a powder formulation of human glucagon for the rescue treatment of hypoglycemia packaged in a user-friendly, single-use, nasal dosing device that delivers 3 mg glucagon powder for absorption through the nasal mucosa. The glucagon component of LY900018 is a synthetic single-chain, 29-amino-acid polypeptide identical to human glucagon. LY900018 is being developed for the rescue treatment of hypoglycemia.

Currently, glucagon in a liquid form lacks physical and chemical stability; thus, marketed products require reconstitution of glucagon powder before the product can be administered through intramuscular (IM) injection. LY900018 combines stable, synthetic glucagon and a nasal dosing device that for effective use obviates reconstitution, injection, and moreover, patient inhalation. Because of these advantages, LY900018 may offer a significant improvement in the treatment of severe hypoglycemia occurring outside of the hospital setting.

The aim of this study I8R-JE-IGBJ (IGBJ) is to compare LY900018 with IM glucagon (IMG) with respect to the proportion of patients who achieved treatment success during the controlled insulin-induced hypoglycemia in Japanese patients with type 1 diabetes mellitus (T1DM) and patients with type 2 diabetes mellitus (T2DM). Treatment success is defined as an increase in plasma glucose (PG) concentration to ≥70 mg/dL or an increase of ≥20 mg/dL from the PG nadir within 30 minutes after receiving glucagon, without the patient receiving additional treatments to increase PG. The nadir is defined as the minimum PG concentration at the time of or within 10 minutes following glucagon administration. The design and conduct of Study IGBJ are similar to the completed Phase 3 Study I8R-MC-IGBC (IGBC) (Rickels et al. 2016) and the planned Phase 1 Study I8R-MC-IGBI.

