5.4. Scientific Rationale for Study Design

This study design involves an open-label assessment of 3 mg LY900018 compared to 1 mg of the marketed IMG (GlucaGen). The study will be open label because the different administration routes (ie, intranasal and IM) cannot be blinded. The use of a crossover design allows each patient to serve as his or her own control, thereby reducing variability. The washout period of 3 to 14 days is considered sufficient based on the short half-life of LY900018 (t_{1/2} = approximately 25 minutes). Since the critical role of glucagon in the treatment of severe hypoglycemia is to raise the PG level sufficiently to restore cognition to the point where oral carbohydrate can be ingested, treatment success is defined either as an increase in PG returning to normal level of ≥70 mg/dL or an increase of ≥20 mg/dL from the PG nadir within 30 minutes after receiving glucagon, without the patient receiving additional actions to increase glucose. It is believed that an expected PG nadir of approximately 50 mg/dL (approximately 5 minutes after stop of insulin infusion at 60 mg/dL) is low enough to generate clinical symptoms in most participants and is high enough to avoid impairment of consciousness. The primary analysis includes both patients with T1DM and T2DM since it is expected that the proportion of treatment success is similar between patients with T1DM and T2DM.

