7.1. Treatment Administered

This study involves a comparison of 3 mg of LY900018 administered once nasally to 1 mg glucagon administered IM (comparator). Table IGBJ.2 shows the study treatment information.

Table IGBJ.2. Study Treatments

Treatment Name	LY900018	GlucaGen			
Dosage Formulation	Dry powder	Dry powder			
Dosage Levels	3 mg glucagon	1 mg glucagon			
Route of Administration	Intranasal	Intramuscular			
Dosing Instructions	Administer a single nasal dose upon	Administer a single intramuscular			
	hypoglycemia onset	injection upon hypoglycemia onset			

The procedure for insulin-induced hypoglycemia will require an IV infusion of diluted human regular insulin (0.3 U/mL by diluting 15 U human regular insulin [100 U/mL] into 50 mL saline). Details regarding hypoglycemia induction and glucagon administration procedures are included in Sections 9.2.1 and 9.2.2, respectively.

The investigator or designee is responsible for:

- explaining the correct use of the investigational products to the site personnel
- verifying that instructions are followed properly
- maintaining accurate records of investigational product dispensing and collection
- and returning all unused medication to Lilly or its designee at the end of the study

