9.4 Pharmacokinetic Assessment

9.4.1 Pharmacokinetic Analysis

Pharmacokinetic parameter estimates will be determined using non-compartmental procedures in validated software program (Phoenix WinNonlin Version 6.4 or later).

Plasma concentrations of glucagon will be used to determine the following PK parameters following LY900018 and GlucaGen administration, when possible:

Final, 01 Feb 2018 Page 12 of 26

Parameter	Units	Definition
AUC(0-4)	pmol.h/L	area under the concentration versus time curve from time zero to 4 hours post-dose
$AUC(0-t_{last})$	pmol.h/L	area under the concentration versus time curve from time zero to time t, where t is the last time point with a measurable concentration
$AUC(0-\infty)$	pmol.h/L	area under the concentration versus time curve from time zero to infinity
$\%$ AUC(t_{last} - ∞)	%	percentage of $AUC(0-\infty)$ extrapolated
C_{max}	pmol/L	maximum observed drug concentration
t_{max}	h	time of maximum observed drug concentration
$t_{1/2}$	h	half-life associated with the terminal rate constant (λz) in non-compartmental analysis
CL/F	L/h	apparent total body clearance of drug calculated after extra-vascular administration
V _z /F	L	apparent volume of distribution during the terminal phase after extra-vascular administration
V _{ss} /F	L	apparent volume of distribution at steady state after extra-vascular administration

The following PK parameters will also be calculated using baseline-adjusted (ie, change from baseline) concentrations of glucagon: AUC, C_{max} , and t_{max} . Baseline glucagon concentrations will be concentrations from samples obtained immediately prior to glucagon dosing (ie, predose).

Additional PK parameters may be calculated, as appropriate. The software and version used for the final analyses will be specified in the clinical study report. Any exceptions or special handling of data will be clearly documented within the final study report.

Formatting of tables, figures and abbreviations will follow the Eli Lilly Global PK/PD/TS Tool: NON-COMPARTMENTAL PHARMACOKINETIC STYLE GUIDE. The version of the tool effective at the time of PK analysis will be followed.

General PK Parameter Rules

- Actual sampling times will be used in the final analyses of individual PK parameters, except for non-bolus pre-dose sampling times which will be set to zero.

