- C_{max} and t_{max} will be reported from observed values. If C_{max} occurs at more than one time point, t_{max} will be assigned to the first occurrence of C_{max} .
- AUC parameters will be calculated using a combination of the linear and logarithmic trapezoidal methods (linear-log trapezoidal rule). The linear trapezoidal method will be applied up to t_{max} and then the logarithmic trapezoidal method will be used after t_{max}. The minimum requirement for the calculation of AUC will be the inclusion of at least three consecutive plasma concentrations above the lower limit of quantification (LLOQ), with at least one of these concentrations following C_{max}.

Final, 01 Feb 2018 Page 13 of 26

- AUC(0-∞) values where the percentage of the total area extrapolated is more than 20% will be flagged. Any AUC(0-∞) value excluded from summary statistics will be noted in the footnote of the summary table.
- Half-life (t½) will be calculated, when appropriate, based on the apparent terminal loglinear portion of the concentration-time curve. The start of the terminal elimination phase for each subject will be defined by visual inspection and generally will be the first point at which there is no systematic deviation from the log-linear decline in plasma concentrations. Half-life will only be calculated when a reliable estimate for this parameter can be obtained comprising of at least 3 data points. If t½ is estimated over a time window of less than 2 half-lives, the values will be flagged in the data listings. Any t½ value excluded from summary statistics will be documented in the footnote of the summary table.
- A uniform weighting scheme will be used in the regression analysis of the terminal loglinear portion of the concentration-time curve.
- The parameters based on observed C_{last} will be reported.

Individual PK Parameter Rules

- Only quantifiable concentrations will be used to calculate PK parameters with the exception of special handling of certain concentrations reported below the lower limit of quantitation (BQL). Plasma concentrations reported as BQL will be set to a value of zero when all of the following conditions are met:
 - The compound is non-endogenous.
 - The samples are from the initial dose period for a subject or from a subsequent dose period following a suitable wash-out period.
 - The time points occur before the first quantifiable concentration.

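### SAP 9.4.1 lists Vss/F for nasal and intramuscular glucagon, but without an intravenous reference it cannot be identified, and the usual calculation overstates it

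*SAP*

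**What the plan says.** SAP 9.4.1 introduces its parameter table with: "Plasma concentrations of glucagon will be used to determine the following PK parameters following LY900018 and GlucaGen administration, when possible". The table includes CL/F, Vz/F and Vss/F, the last defined as the "apparent volume of distribution at steady state after extra-vascular administration". On method, the same section says: "Pharmacokinetic parameter estimates will be determined using non-compartmental procedures in validated software program". It gives no formula for Vss/F, and no mean absorption time, deconvolution step or absorption model.

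Protocol 7.1 fixes the routes: "This study involves a comparison of 3 mg of LY900018 administered once nasally to 1 mg glucagon administered IM (comparator"). Neither document describes an intravenous glucagon dose.

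SAP 9.4.2 says that the PK parameters will be statistically analysed, listed and summarized by diabetes type and overall. The mixed model in that section names Cmax and AUC as examples only.

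Protocol 10.3.3.1 makes Cmax, AUC and Tmax the primary PK parameters. It allows an apparent volume of distribution to be reported and does not name a steady-state volume.

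**The concern.** A non-compartmental steady-state volume is clearance multiplied by the mean residence time after intravenous input. After a nasal or intramuscular dose, the quantity that can be observed, AUMC/AUC, is that residence time plus the mean time the drug takes to be absorbed. One extravascular profile gives only the sum. Neither more patients nor baseline correction of the concentrations separates the two terms.

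What is at stake is interpretation. Characterizing the PK profile of LY900018 compared with intramuscular glucagon is a secondary objective, and Vss/F would stand in that comparison. Protocol 3.1 describes the glucagon in LY900018 as a "29-amino-acid polypeptide identical to human glucagon", and the comparator is also glucagon. A reader who saw different values of Vss/F by route might look for a distributional reason, when slower or faster absorption alone can produce the difference.

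**Working it through.** The documents give no value for Vss/F, MRT or MAT, so there is no planned figure to reproduce.

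**Inputs**
- Half-life of LY900018: about 25 min (Protocol 5.4, which says the washout "is considered sufficient based on the short half-life of LY900018"). It is given for LY900018 only, and the protocol does not say whether it reflects elimination or absorption.
- PK sampling: 12 post-dose samples from 5 to 240 min (Protocol Section 2, Schedule of Activities).
- AUC rule: "AUC parameters will be calculated using a combination of the linear and logarithmic trapezoidal methods (linear-log trapezoidal rule"), linear up to tmax and logarithmic after it (SAP 9.4.1).
- Assumed, because the documents do not give them: one compartment, first-order input, and Tmax of 10 to 30 min (or, as an alternative, MAT directly).

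**Formula**
- Vss/F = (CL/F) × MRT, and AUMC/AUC = MRT + MAT after extravascular input.
- Hence (CL/F) × AUMC/AUC = (Vss/F) × (1 + MAT/MRT).
- In one compartment, MRT = 1/ke and MAT = 1/ka, with ka solved from ln(ka/ke)/(ka − ke) = Tmax.

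**Case A: the 25 min is elimination.** ke = ln 2/25, so MRT = 25/0.693 = 36.1 min.

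| Assumed Tmax (min) | MAT (min) | 1 + MAT/MRT |
|---|---|---|
| 10 | 4.1 | 1.11 |
| 15 | 7.6 | 1.21 |
| 20 | 12.2 | 1.34 |
| 30 | 25.2 | 1.70 |

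With MAT assumed directly at 5, 10, 15, 20 and 30 min, the factor is 1.14, 1.28, 1.42, 1.55 and 1.83.

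**Case B: the 25 min is absorption (flip-flop).** The two rate constants change places, so MAT = 36.1 min and MRT takes the values in the MAT column above. For Tmax of 10, 15, 20 and 30 min:
- Vss/F is overstated by a factor of 1 + 36.1/MRT = 9.9, 5.7, 4.0 and 2.4.
- Vz/F = (CL/F)/λz is also inflated, because λz is now the absorption rate. Its factor is 36.1/MRT = 8.9, 4.7, 3.0 and 1.4, from unrounded MRT.

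**Check on the planned sampling times.** Simulated Case A profiles, sampled at the protocol times and integrated by the SAP's rule, gave:

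| MAT (min) | Vss/F ratio | Vz/F ratio |
|---|---|---|
| 5 | 1.17 | 1.01 |
| 10 | 1.30 | 1.01 |
| 15 | 1.43 | 1.01 |
| 30 | 1.85 | 1.18 |

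The Vss/F ratios agree closely with the formula. These runs had no endogenous glucagon. Adding an assumed constant baseline of 0.5% to 2% of Cmax raised both volumes: at MAT 5 min, Vss/F went to 1.24–1.44 and Vz/F to 1.40–2.00. That is a separate issue from absorption time, but it shows that Vz/F has limits of its own.

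**Between routes.** If MAT were 5 min by one route and 15 min by the other, with the same MRT and F, Vss/F would differ by 1.42/1.14, or about 24%, from absorption alone.

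**The case against.** Four arguments on the other side deserve weight.

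1. *The SAP does not say how Vss/F will be computed.* It gives no formula, lists the parameter only where it can be determined, and says that special handling will be documented in the study report. A reader might infer that a wrong value is certain to be reported. The documents do not support that: the overstatement assumes the usual uncorrected calculation. What remains is that Vss/F cannot be identified from these data whatever formula is used. The qualifier reads as one about data availability, and a value can be calculated whenever AUC, AUMC and a terminal slope are available.

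2. *A route difference is not evidence of error.* It is tempting to argue that one molecule must have one Vss/F, so a nasal–intramuscular difference would expose the flaw. It would not. The parameter is divided by F, F need not be the same for the two routes, and a correctly estimated Vss/F could differ for that reason, as could CL/F and Vz/F. The valid complaint is narrower: absorption time adds a further difference that cannot be separated.

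3. *The flip-flop multiples affect the remedy too.* If the terminal slope is absorption, Vz/F is inflated along with Vss/F, so deleting Vss/F alone does not settle the matter. This stands, and it is why the fix below adds a note on Vz/F.

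4. *Little depends on it.* The PK endpoints are AUC, Cmax and Tmax, and the primary analysis uses plasma glucose only. This also stands. A footnote could replace deletion, but it would keep a row that has no usable interpretation.

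**Conclusion.** Vss/F as listed in SAP 9.4.1 is not identifiable, because both routes are extravascular, the analysis is non-compartmental and there is no intravenous reference. If it is computed as (CL/F) × AUMC/AUC, the bias is upward by the factor 1 + MAT/MRT.

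The size is about 11% to 70%. That range assumes that the 25-minute half-life is elimination, applies to both products, and goes with a one-compartment profile, first-order input and a Tmax of 10 to 30 minutes. Only the half-life comes from the documents, and they state it for LY900018 alone. The factor of 2.4 to 9.9 applies only if the 25 minutes reflects absorption. The documents do not say that it does, so those multiples should not be quoted as the expected error.

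A reader might also infer that the PK comparison as a whole, or the non-inferiority conclusion, is compromised. Neither follows. AUC, Cmax and Tmax do not use Vss/F, and no endpoint or decision depends on it. This is a minor correction to a parameter list.

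**What to change.** - Delete the Vss/F row from the parameter table in SAP 9.4.1 and its entry in the abbreviation list (SAP Section 2).
- Keep CL/F and Vz/F, with a table note that Vz/F assumes the terminal slope reflects elimination.
- If residence time is of interest, report AUMC/AUC labelled 'mean residence time including absorption'.

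The cost is one table row, one abbreviation and one footnote. No protocol commitment is lost: Protocol 10.3.3.1 makes an apparent volume of distribution optional, and Vz/F covers it. If the sponsor prefers to keep Vss/F, the minimum is a footnote saying that it is not corrected for absorption time and is not comparable between routes.

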9.6.1. Bioanalysis

Samples will be analyzed at a laboratory approved by the sponsor and stored at a facility designated by the sponsor.

Concentrations of glucagon will be assayed using a validated liquid chromatography with tandem mass spectrometry method.

Bioanalytical samples collected to measure investigational product concentrations will be retained for a maximum of 1 year following last patient visit for the study.

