- All other BQL concentrations that do not meet the above criteria will be set to missing.
- Also, where two or more consecutive concentrations are BQL towards the end of a profile, the profile will be deemed to have terminated and therefore any further quantifiable concentrations will be set to missing for the calculation of the PK parameters unless it is considered to be a true characteristic of the profile of the drug.

Individual Concentration vs. Time Profiles

- o Individual concentrations will be plotted utilizing actual sampling times.
- The terminal point selections will be indicated on a semi-logarithmic plot.
- o Baseline corrected concentration plots will also be presented

Average Concentration vs. Time Profiles

- The average concentration profiles will be graphed using scheduled (nominal) sampling times.
- o The average concentration profiles will be graphed using arithmetic average concentrations.
- o Quantifiable concentrations will be used to calculate average concentrations.

Final, 01 Feb 2018 Page 14 of 26

- \circ Concentrations at a sampling time exceeding the sampling time window specified in the protocol, or \pm 10%, will be excluded from the average concentration profiles.
- Concentrations excluded from the mean calculation will be documented in the final study report.
- O A concentration average will be plotted for a given sampling time only if 2/3 of the individual data at the time point have quantifiable measurements that are within the sampling time window specified in the protocol or ± 10%. An average concentration estimated with less than 2/3 but more than 3 data points may be displayed on the mean concentration plot if determined to be appropriate and will be documented within the final study report.

Treatment of Outliers during Pharmacokinetic Analysis

Application of this procedure to all pharmacokinetic analyses is not a requirement. Rather, this procedure provides justification for exclusion of data when scientifically appropriate. This procedure describes the methodology for identifying an individual value as an outlier for potential exclusion, but does not require that the value be excluded from analysis. The following methodology will not be used to exclude complete profiles from analysis.

Data within an Individual Profile

A value within an individual profile may be excluded from analysis if any of the following criteria are met:

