9.6.5 Electrocardiogram (ECG)

Triplicate ECG data will be obtained directly from the 12-lead ECG traces. These data include the PR, QT, QTcB intervals, QRS duration and heart rate, where QTcB is the QT interval corrected using Bazett's formula. In addition, the QT interval corrected using Fridericia's formula (QTcF) will be calculated as follows:

$$QTcF = \frac{QT}{\sqrt[3]{60/HR}}$$

The mean of the triplicate data will be used for subsequent calculations. The ECG data will be summarized by treatment together with changes from baseline, where baseline is defined as Day 1 predose of each period. Figures of mean ECG data and mean changes from baseline will be presented by treatment. The frequency of subjects with a maximum increase from baseline in QTcF interval will be summarized for each treatment according to the following categories: >30 ms and >60 ms. In addition, the frequency of subjects with QTcF postdose values, according to the following categories: >450 ms, >480 ms and >500 ms, will be summarized by treatment.

All timepoints will be presented on summary tables and figures.

A plasma LY900018 concentration-QT analysis will be performed to assess the changes from baseline (Day 1 predose of each period) QTcF interval relative to plasma LY900018. BLQ

Final, 01 Feb 2018 Page 20 of 26

LY900018 concentration data will be imputed to 50% of the LLOQ for the purposes of the analysis. The analysis will be performed by plotting change from baseline QTcF against LY900018 concentrations, including all post dosing timepoints. The plot will be produced separately for each treatment and diabetes type.

A mixed effects analysis model will be performed on the change from baseline QTcF values and will include LY900018 concentration as a covariate and subject as a random effect. The results of the model and associated 90% CI will be fitted on the plot and the p-value for the slope reported.

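### A predose glucagon value below quantification is set to missing, so that period's baseline-adjusted AUC and Cmax cannot be derived

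*SAP*

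**What the plan says.** SAP 9.4.1, under its rules for individual PK parameters, has two branches for BQL values. The first reads "Plasma concentrations reported as BQL will be set to a value of zero when all of the following conditions are met". Three conditions follow: "The compound is non-endogenous"; the sample comes from the initial dose period or follows a suitable washout; and "The time points occur before the first quantifiable concentration". The second branch is the default: "All other BQL concentrations that do not meet the above criteria will be set to missing".

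The same section plans AUC, Cmax and tmax on change-from-baseline glucagon concentrations, in addition to the unadjusted set, and defines the baseline: "Baseline glucagon concentrations will be concentrations from samples obtained immediately prior to glucagon dosing (ie, predose". Protocol 10.3.3.1 agrees. Neither document names a substitute baseline, although the Schedule of Activities also collects a PK sample before hypoglycemia induction in each period.

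On the analyte, Protocol 3.1 states: "The glucagon component of LY900018 is a synthetic single-chain, 29-amino-acid polypeptide identical to human glucagon". Protocol 9.6.1 states: "Concentrations of glucagon will be assayed using a validated liquid chromatography with tandem mass spectrometry method".

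SAP 9.6.5 has a different rule, confined to the concentration-QT analysis, where BQL "concentration data will be imputed to 50% of the LLOQ".

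**The concern.** The BQL rule appears to be written for a drug that is absent from the body before dosing. Glucagon is not such a compound, and the plan to subtract a baseline acknowledges this. The first condition is therefore false for every sample, and a BQL predose value always goes to missing. That value is the only defined baseline, so one missing number removes a whole period from adjusted AUC and Cmax.

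These are also the periods where the adjustment matters least: the baseline is known to be below the LLOQ, so the correction is the smallest in the data set. Characterising the PK of LY900018 against IMG is a secondary objective, and SAP 9.4.2 analyses PK by diabetes type as well as overall, with only 30 completers per type as the planned minimum. At stake is precision in that comparison, and an analyst choosing a remedy after seeing the data.

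**Working it through.** The plan states no figure that depends on this rule, so there is nothing to reproduce. The check has four steps.

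**1. The rule as logic.** There are three yes/no conditions, hence 2 × 2 × 2 = 8 combinations. A BQL value becomes zero in exactly 1 of the 8, and that one requires a non-endogenous compound. In all 4 combinations with an endogenous compound the result is missing.

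**2. Effect on the adjusted profile.** The adjusted concentration is C(t) − C(predose). With C(predose) missing, it is missing at every time point, so adjusted AUC and Cmax cannot be derived. Adjusted tmax is different: subtracting a constant does not move the time of the maximum, so it equals unadjusted tmax, which is still available. Unadjusted Cmax is also available.

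Unadjusted AUC is left without a stated time-zero concentration. The first post-dose sample is at 5 minutes, so on the linear rule any value from 0 to the LLOQ at time zero changes the area by at most ½ × (5/60) h × LLOQ ≈ 0.04 h × LLOQ, which is negligible.

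**3. How much is lost.** The LLOQ and the BQL rate are not in the documents. Let q be the assumed share of predose samples that are BQL, with 66 completers and 132 periods.
- Periods lost = 132q.
- Patients without a complete pair = q if a patient's two periods are fully correlated, and 1 − (1 − q)² if they are independent.

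| q (assumed) | Periods lost of 132 | Without complete pair, correlated | Without complete pair, independent |
|---|---|---|---|
| 5% | 6.6 | 5% (3.3 of 66) | 9.75% (6.4 of 66) |
| 10% | 13.2 | 10% (6.6 of 66) | 19% (12.5 of 66) |

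At q = 10%, a diabetes-type stratum of 30 would have between 30 × 0.10 = 3 and 30 × 0.19 = 5.7 patients without a complete pair.

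**4. Error from imputing instead.** Replace the missing baseline by b, with 0 ≤ b ≤ LLOQ.
- Adjusted Cmax = Cmax − b, so it moves by at most one LLOQ over the whole range.
- Adjusted AUC(0-4) falls by about 4 h × b on the linear trapezoidal rule, so it moves by at most about 4 h × LLOQ.

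An illustration uses assumed concentrations of 200, 600, 900, 1000, 950, 850, 600, 420, 300, 120, 50 and 10 pmol/L at the scheduled times from 5 to 240 minutes, with the adjusted time-zero value equal to 0:

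| Assumed LLOQ (pmol/L) | Adjusted Cmax, b = LLOQ to b = 0 | Adjusted AUC(0-4), linear (pmol·h/L) |
|---|---|---|
| 1 | 999 to 1000 | 809.0 to 812.9 |
| 5 | 995 to 1000 | 793.1 to 812.9 |
| 10 | 990 to 1000 | 773.3 to 812.9 |

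The SAP uses the logarithmic rule after tmax, which is more sensitive in the tail. On the same profile with that rule, adjusted AUC runs from 786.0 to 790.6 at LLOQ 1 (4.5 h × LLOQ) and from 767.1 to 790.6 at LLOQ 5 (4.7 h × LLOQ). The 4 h figure is thus a linear-rule bound. The log rule can exceed it, and does so most when late concentrations sit close to the LLOQ.

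**The case against.** The strongest reply is that little is at risk. Much of it stands.

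- **Two stronger readings fail: that patients drop out of the comparison, and that it is biased.** SAP 9.4.2 analyses AUC and Cmax in a mixed model with a random patient effect, so a patient who loses one period still contributes the other. A patient is removed only if both predose samples are BQL. The predose value precedes glucagon, and treatment sequence is randomised, so nothing in the documents suggests that the loss differs between LY900018 and IMG.
- **Adjusted tmax is not really lost**, for the reason given in the working.
- **SAP 9.6.5 does not contradict SAP 9.4.1.** A reader might infer that the plan treats the same value in two ways. The 50% rule serves a concentration-QT plot and model built on post-dose time points. It does not govern a PK baseline.
- **The non-endogenous condition has a purpose.** A BQL result for a hormone should not simply be taken as zero. That is a reason not to impute zero as the main rule, but it does not justify discarding a value known to lie in a bounded interval.
- **The unadjusted parameters nearly supply the answer.** With a baseline below the LLOQ, adjusted and unadjusted Cmax differ by less than one LLOQ. The adjusted set is nevertheless planned in both documents, and its estimates would rest on fewer profiles.
- **Exceptions can be documented.** SAP 9.4.1 says that special handling will be recorded in the study report. That permits a choice after the data are seen and is not a pre-specified rule.

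**Conclusion.** The point holds as a conditional defect in a secondary analysis. As written, any BQL predose glucagon value is set to missing, and that period's adjusted AUC and Cmax cannot be computed. The loss is selective, since it takes the periods with the lowest endogenous glucagon, and it costs precision. The primary endpoint and unadjusted Cmax and tmax are unaffected.

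The size is unknown. The 5% and 10% rates are assumptions, and the independent-periods figures are the upper end: if low glucagon is a stable patient trait, the correlated figures are closer. If every predose sample is quantifiable, nothing is lost. A reader might extrapolate to far higher BQL rates and conclude that most patients are affected; the documents give no support for such rates.

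**What to change.** Add one sentence to SAP 9.4.1: for glucagon in this study, a BQL predose value is set to 50% of the LLOQ, both as the baseline and as the time-zero concentration, with the adjusted AUC and Cmax analyses repeated using 0 and the LLOQ. State the assay LLOQ alongside, and report the number of imputed baselines by treatment and period.

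The cost is an imputed baseline. Over the full range from 0 to the LLOQ it can shift adjusted Cmax by at most one LLOQ and adjusted AUC(0-4) by about 4 h × LLOQ (somewhat more under the SAP's log rule in the tail). The two sensitivity analyses show that range directly. No new sample or procedure is needed.
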